### 3.A NUMBER OF PATIENTS / ENROLMENT/ FOLLOW-UP PERIOD

This study will include a total of 306 patients (*153 in each group, see section 7.B.2*), randomly assigned to one of the two study groups detailed in section 4.A by centre, smoking status and need for respiratory assistance (*i.e., home oxygen therapy or Non-Invasive Ventilation*) for chronic respiratory failure at Selection.

The planned total study duration is 52 months, including a 38-month enrolment period and a 14-month follow-up for each randomised patient.

### 3.B INCLUSION CRITERIA

Patients who fulfil all the inclusion criteria are eligible for study participation. The criteria for inclusion are:

- 1) Male or female patient aged  $\geq 35$  years old,
- 2) Current or ex-smoker with a smoking history  $\geq 10$  pack-years,
- 3) Patient having diagnosed COPD stage III or IV according to GOLD criteria: a post-bronchodilator\* FEV1/FVC ratio  $\leq 70\%$  and a post-bronchodilator\* FEV1  $< 50\%$  of predicted value, assessed by pulmonary function tests performed less than 12 months prior to Selection. Patient can be treated with all relevant COPD treatment, including home oxygen therapy and mechanical ventilation,  
\* measured 30 min after the inhalation of an adequate dose of a short-acting inhaled bronchodilator, e.g., 400 µg salbutamol or equivalent,
- 4) Patient who has had at least one COPD exacerbation leading to hospitalisation in the year before Selection,
- 5) Patient living within less than 2-hour transportation of the investigational centre,
- 6) Patient able to read and speak native language of his/her study country,
- 7) Patient having a touch tone telephone,
- 8) Patient willing and able to complete the requirements of the study including the signature of the Informed Consent after full explanation of the study by the investigator prior to participation.

### 3.C EXCLUSION CRITERIA

If any of the exclusion criteria are fulfilled, potential patients are not eligible for study participation. The criteria for exclusion are:

- 9) Patient previously randomised in the study,
- 10) Patient on LTOT for another reason than COPD, *e.g.,* for a concomitant significant chronic disease such as asthma, diffuse bronchiectasis including cystic fibrosis, sarcoidosis, lung fibrosis, kyphoskoliosis, neuromuscular disease, severe left chronic cardiac failure, ...,

- 11) Patient with limited probability of survival (< 6 months),
- 12) Patient with a tracheostomy,
- 13) Patient receiving long term oral corticosteroids therapy (*defined as continuous use of > 10 mg of prednisone or equivalent per day for more than 6 weeks. Successive courses of oral corticosteroids separated by a period of less than 7 days will be considered as continuous use*),
- 14) Patient who has, in the knowledge of the investigator, a condition which could limit compliance to study procedures, such as:
  - 14.a) Alcohol abuse,
  - 14.b) Drug (*e.g., cannabis, cocaine, ...*) abuse,
  - 14.c) Solvent abuse,
  - 14.d) Dementia,
  - 14.e) Uncontrolled psychiatric illness,
- 15) Patient not covered by a health insurance,
- 16) Patient living in a medicalised nursing home,
- 17) Patient who participated in another interventional clinical trial within 30 days before Selection.

### 3.D WITHDRAWAL CRITERIA

Reasons for **premature discontinuation of the allocated management strategy** include:

- Patient moving for long term stay in a medicalised nursing home,
- Any lack of compliance to the study procedures which can compromise the study progress, and, in particular, for the Intervention group only:
  - a) Absence of phone call to the study vocal server to report clinical status for more than 1 month for another reason than being away from home,
  - b) Refusal or inability to follow the four individual home education sessions before Visit 1 as detailed in section 4.B.3.1.

Whenever possible, in case of premature discontinuation of the allocated management strategy, patients will be followed up until Month 12 as initially planned (*by regular visits at the investigational centre and standardised phone interviews, as detailed in section 4.B.3.2*).

Reasons for **study premature withdrawal** include:

- Patient moving away from the geographic area of the investigational centre resulting in the patient's inability to attend study visits,
- Withdrawn consent as described in the Patient Informed Consent,

- Death.

The reason, date and time for premature discontinuation of the allocated management strategy and/or study premature withdrawal will be recorded in the electronic Case Report Forms (e-CRF) of the patients concerned by their investigator. Survival data until Month 12 will be collected unless the patient disagrees.

**The patient will be replaced** only if premature discontinuation of the allocated management strategy or study premature withdrawal occurs before the end of Visit 1 (*see section 4.B.3.1*).

## 4. INVESTIGATIONAL PLAN

[figure not shown]
### 4.A STUDY DESIGN

This is an international, multicentre, open, randomised, prospective, controlled, parallel-group Phase IV study. It will be conducted in four (4) countries (France, Germany, Italy and Spain) and approximately forty-five (45) investigational centres.

Included patients will be randomly assigned by centre, smoking status and need for respiratory assistance (*i.e.*, *home oxygen therapy or Non-Invasive Ventilation*) for chronic respiratory failure at Selection to one of the two (2) study groups:

- Either Home-Based COPD Management group (*Intervention group*),
- Or the Usual COPD Education and Patient Follow-Up group (*Control group*).

**Figure 1:** Schematic Study Design

## 4.B STUDY PLAN

The participants will follow the three (3) consecutive study periods as detailed below:

- *Selection Period*: period during which the patient is evaluated for inclusion/exclusion criteria and, if eligible, randomised in to one of the two (2) study groups (*Visit 0*),
- *Run-In Period*: period from randomisation to Visit 1 (*visit at the investigational centre*), during which all medical evaluations will be performed and, for patients randomised in the Intervention group, the four (4) individual home education sessions will be performed. This period will last 5 weeks ( $\pm 5$  days) following randomisation.
- *Follow-Up Period*: 12-month period from the end of the *Run-In Period* (*end of Visit 1*) including 4 evaluation visits at the investigational centre (*every 3 months*) and 4 standardised phone interviews with the centre between evaluation visits. Moreover, for patients randomised in the Intervention group, the *Follow-Up Period* will include education sessions every month (*alternatively group and phone sessions*) and an at least weekly prospective telephone follow-up.

Patients randomised in the Control group will receive, during their *Run-In* and *Follow-Up Periods*, the usual COPD education and follow-up as per investigational centre routine practice.

### 4.B.1 Selection of patients

#### 4.B.1.1. Recruitment

After receiving local ethics committees and national competent authority approvals (*see section 9.A*), patients will be recruited by the investigators of the participating investigational centres among their patients with GOLD III/IV COPD. After full explanation of the study by the investigator, signed and dated Informed Consent will be obtained from patients who accept to participate to the study (*see section 9.B*), before the onset of any study specific procedures.

#### 4.B.1.2. Selection (*Visit 0*)

Patients who meet all inclusion criteria and none of the exclusion criteria (*see sections 3.B and 3.C*), *i.e.*, all eligible patients, will be included. A 3-digit patient number (*selection number*) will be assigned in sequential order (*001, 002, ...*), in each investigational centre separately, to each patient having signed and dated his/her Informed Consent.

#### **During Visit 0, the investigator will:**

- Perform a physical examination including vital signs, pulse oximetry, height and weight,
- Randomise the patient (*see section 4.B.2*),
- Schedule an appointment for Visit 1, five (5) weeks ( $\pm 5$  days) after Visit 0,
- Schedule all medical evaluations and laboratory samplings to be performed between Visit 0 and Visit 1,
- Provide the patient with the “Patient’s Study Diary”\*,

- Send a standardised education request form to the health counsellor and provide the patient with a fulfilled written action plan (*for patients randomised to the Intervention group only*).

\* "Patient's Study Diary" contains the following: schedule of planned contacts (*visits at the investigational centre, phone interviews, and for patients in the Intervention group, education sessions*); investigator's name and telephone number, and all useful contacts; weekly forms for the patient to record any use of health care services (*medical and paramedical consultations, attendances at emergency departments, hospitalisations*); and, for patients of the Intervention group only, space to report the date and results of their home respiratory self-assessments (*SpO2, pulse rate, FEV1 and body temperature as detailed in sections 5.A.1.2 and 5.A.4*).

**During Visit 0**, for each eligible patient, the investigator will record the following data in the e-CRF:

- Date of Visit 0 and date of signature of Patient Informed Consent,
- Date of birth, sex, height and weight,
- Results of the physical examination including vital signs (*i.e., systolic and diastolic blood pressures*) and pulse oximetry (*pulse rate and SpO2*) on room air and also, only for patients on oxygen therapy, on oxygen,
- Social conditions (*civil status, area of residence and type of residence*),
- COPD history including:
  - ✓ Date of diagnosis and suspected cause of COPD,
  - ✓ Smoking status and history (*i.e., current or ex-smoker, the later being defined as patients who have stopped smoking for at least 6 months prior to Visit 0, current number of cigarettes smoked per day, estimated number of pack-years, smoking start and stop dates, if applicable*),
  - ✓ Results and date of the most recent pulmonary function tests available (*including Forced Expiratory Volume in 1 second (FEV1) and Forced Vital Capacity (FVC), as both raw values and percentages of predicted values, as well as FEV1/FVC ratio*), performed in stable state less than one year prior to Visit 0,
  - ✓ Patient-reported number of previous moderate and severe COPD exacerbations (*as defined in section 6.A.2.2*) having occurred in the year prior to Visit 0,
- Medical and surgical history not related to COPD and concomitant diseases,
- COPD and non-COPD medication, including oxygen therapy, CPAP, Non-Invasive Ventilation and vaccines performed in the year prior to Visit 0 (*see section 5.D*), and contraception method used, if applicable,
- Start date and criteria for oxygen prescription, if applicable:
  - ✓ Results and date of the most recent resting arterial or capillary blood gases on room air available, performed in stable state (*defined by a period of at least 3 weeks without exacerbation*), within 12 months prior to Visit 0 (*including pH, PaO2, PaCO2, HCO3 and SaO2*),

- ✓ Presence/absence of the following (*including dates of measurement or assessment, when present*): pulmonary hypertension, peripheral oedema and haematocrit > 55%.

#### **4.B.2 Method of assigning patients to study groups**

According to their smoking status, their need for respiratory assistance (*i.e., home oxygen therapy or Non-Invasive Ventilation*) for chronic respiratory failure at Selection and their investigational centre, included patients will be randomly assigned to either the Intervention group or the Control group, according to a computer generated randomisation list pre-specified prior to the study start. The randomly allocated study group to a given included patient and the corresponding 4-digit randomisation number will be attributed in sequential numerical order by the study dedicated telephone Interactive Voice Response System (IVRS). This randomisation number will be used throughout the study as the identification number for all randomised patients.

The randomly allocated study group and the corresponding 4-digit randomisation number will be notified to the investigator through the IVRS and they will be confirmed automatically *via* an e-mail and/or fax sent to the investigator. The investigator will print the randomisation confirmation e-mail/fax and file it in the investigator binder.

Neither the patient nor the study personnel of the investigational centre will be blinded as to the study group allocated, after randomisation.

#### **4.B.3 Study implementation**

##### **4.B.3.1. Run-In Period**

At the end of the *Selection Period*, randomised patients will start the *Run-In Period*. During the *Run-In Period*, patients will undergo medical evaluations and laboratory sampling to evaluate their COPD at study entry. Patients will receive COPD education according to their randomly allocated study group, *i.e.*, either the Intervention group or the Control group. The *Run-In Period* will last 5 weeks ( $\pm 5$  days) and will finish when Visit 1 is completed.

**Exceptionally, the duration of the *Run-In Period* may be prolonged by 4 supplemental weeks** *i)* in the occurrence of a medical event which is expected to be resolved within 4 weeks (*for example, a COPD exacerbation starting during the Run-In Period*), or *ii)* to allow patients included at hospital discharge to reach sufficient clinical stability to perform the medical tests required and, for patients of the Intervention group, to receive the education sessions in optimal conditions.

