## COPD EDUCATION

**Patients randomised in the Control group** will receive the usual COPD education as per investigational centre routine practice. The content and modalities of each centre will be collected before study initiation, as well as any modifications throughout the study period, if applicable.

**Patients randomised in the Intervention group** will undergo four (4) individual home education sessions, performed on a weekly basis by a community-based health professional (*called for the study 'health counsellor' and detailed in section 5.A.1*):

- The four sessions will be performed before Visit 1, in a minimum of 3 weeks and a maximum of 5 weeks after randomisation.
- Each individual session is planned to last 60 to 90 minutes during which the health counsellor will use specific teaching material in local study language and will give the patient the printed education documents (*handbooks and brochure, as detailed in section 5.A.1.1*) and the study medical devices (*portable pulse oximeter, spirometer and thermometer, as detailed in section 5.A.4*). The patient will also be trained to perform phone calls to the study dedicated vocal server. After each education session, the understanding and skills of the patient will be assessed and a report will be sent by the health counsellor to the investigator concerned.

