#### 4.B.3.2. Follow-Up Period

The *Follow-Up Period* starts at the end of Visit 1 and will last 12 months for each patient.

Patients will undergo during this period:

- **Visits** at the investigational centre every 3 months (*Visits 2 to 5*),
- **Standardised phone interviews** performed by an investigational centre staff member every 3 months between the patient visits at the investigational centre (*Centre phone contacts 1 to 4*),
- And, **for patients randomised in the Intervention group**, education sessions given by a health counsellor every month (*alternatively group and phone sessions*), and an at least weekly prospective telephone follow-up while **for patients randomised in the Control group**, the usual COPD education and follow-up as per investigational centre routine practice.

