### 6.A EFFICACY EVALUATIONS

#### 6.A.1 *Primary efficacy criterion*

The primary efficacy criterion is the **number of unscheduled hospital days, whatever the reason, during the *Follow-Up Period*** for each randomised patient.

Hospitalisations are defined as stays in the following facilities:

- Emergency room, if duration of stay is > 24 hours,
- Intensive care unit, intermediate care unit, surgical or medical wards,
- Nursing facilities following an acute hospital stay.

Scheduled inpatient rehabilitation will not be considered as hospitalisations.

The number of unscheduled hospital days will be calculated for each randomised patient based on the following information recorded by the investigators in the e-CRF for each hospitalisation separately during the *Follow-Up Period*:

- Reason for admission,
- Type of facility,
- Dates of admission and discharge for each facility.

These data will be normalised by total number of days that the patient will have participated in the *Follow-Up Period* to yield the duration of hospitalisations per year, as detailed in section 7.B.3.5.

Each hospitalisation will also be reported as a Serious Adverse Event as defined in section 8.A.

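### The primary hospital-day count starts at a movable Visit 1, so unequal use of the 4-week Run-In extension would remove early hospital days unequally between arms: a small bias, cheaply avoided

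*Protocol*

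**What the plan says.** - **What is counted.** Section 6.A.1 defines the primary criterion as the "number of unscheduled hospital days, whatever the reason, during the" Follow-Up Period.
- **When counting starts.** Under section 4.B.3.2 that period "starts at the end of Visit 1 and will last 12 months for each patient".
- **When Visit 1 falls.** Randomisation is at Visit 0. On the Run-In, section 4.B says "This period will last 5 weeks", with a tolerance of 5 days either way. At Visit 0 the investigator must "Schedule an appointment for Visit 1, five (5) weeks" ahead, with the same tolerance (section 4.B.1.2).
- **Extension.** Section 4.B.3.1 allows 4 further weeks in exceptional cases. The first ground is "in the occurrence of a medical event which is expected to be resolved within 4 weeks", and the example given is a COPD exacerbation that begins in the Run-In. The second covers patients included at hospital discharge: they may need time to become stable enough for the tests and, "for patients of the Intervention group, to receive the education sessions in optimal conditions".
- **Session timing.** The COPD Education part of the same section requires the four home sessions before Visit 1, "in a minimum of 3 weeks and a maximum of 5 weeks after randomisation".
- **Flow chart.** The footnote in section 6.E repeats the extension rule with grounds common to both arms and does not mention the sessions.
- **Blinding.** "Neither the patient nor the study personnel of the investigational centre will be blinded as to the study group allocated, after randomisation" (section 4.B.2).

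**The concern.** The start of the counting window depends on events after randomisation, in a trial whose staff know the allocation. One named trigger, an exacerbation, is the kind of event that the endpoint counts if the patient is admitted. One stated purpose of the extension exists in a single arm.

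A stay in about weeks 5 to 9 is therefore ignored if Visit 1 has been put back and counted if Visit 1 was held on time. If extension were more common in the Intervention group, that group could show fewer hospital days with no effect of the programme, in the trial's single confirmatory test.

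The existing safeguards do not reach this:
- The normalisation in section 7.B.3.5 corrects for length of follow-up. A delayed Visit 1 moves the 12-month window without shortening it.
- The blinded Endpoint Validation Committee (section 6.D) reviews only admissions in the Follow-Up Period.

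**Working it through.** **1. The yardstick.** Section 7.B.2 plans on a difference of 10 days, SD 25, two-sided α = 0.05 and power 0.90 for the Wilcoxon test. With Noether's formula:
- p = Φ(10 / (25√2)) = 0.6114
- n = (1.960 + 1.282)² / (6 × 0.1114²) = 141.2, so 142 per group; the plan states 143
- 143 / (1 − 0.0625) = 152.5, so 153 per group and 306 in all, as stated

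The sample size reproduces and is not affected by this point. The planned 10 days is the scale for judging any bias.

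**2. Range of Visit 1.** Without extension: day 35 − 5 = 30 to day 35 + 5 = 40. With extension: up to day 35 + 28 = 63, or 40 + 28 = 68 at most.

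**3. What a delay does.** Moving Visit 1 from day 35 to day 63 drops days 35–62 and adds days 400–427. The length stays 365 days, so the scaling factor stays at 1. The change for a patient is (hospital days in 400–427) − (hospital days in 35–62). Bias between arms therefore needs two things together: unequal use, and more hospital days in the early slice than in the late one. The second arises when an event triggers the extension or when risk falls after entry.

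**4. Size.** The protocol gives no admission rate, length of stay or extension frequency, so these are assumptions. I simulated no true effect, with admissions varying between patients, mean stay 12 days (SD 14), and admission risk either constant or 2 or 3 times higher just after entry and then declining. Entries are Intervention minus Control, in days per year.

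| | Constant, 1.2 admissions/yr | 2× early, base 1.0/yr | 3× early, base 0.9/yr |
|---|---|---|---|
| Mean yearly days (SD) | 13.8 (23.2) | 12.9 (22.4) | 12.5 (21.9) |
| Patients in hospital during Run-In | 10.3% | 14.2% | 17.3% |
| Of these, extended 50% vs 50% | +0.01 | +0.01 | 0.00 |
| Of these, extended 75% vs 25% | −0.12 | −0.24 | −0.31 |
| Of these, extended 100% vs 0% | −0.25 | −0.45 | −0.63 |
| 30% of Intervention extended regardless of events, no Control | +0.01 | −0.12 | −0.22 |
| All Intervention, no Control | +0.07 | −0.41 | −0.72 |

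Check on the first column: patients in hospital during the Run-In have 4.6 hospital days in days 35–62. The net loss per extended patient is 0.25 / 0.103 = 2.4 days, so about 2.2 days are regained at the far end of the window, because these patients remain at high risk.

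**5. Test level.** With 143 per group and 2,000 runs per setting, the Wilcoxon test rejected in 4.4% to 5.6% of runs. The simulation standard error is √(0.05 × 0.95 / 2000) = 0.5 percentage points, so this range cannot be told apart from 5%.

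**The case against.** The case on the other side is substantial, and most of it stands.

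- Extensions are exceptional. The purpose specific to the Intervention group sits within the ground for patients included at hospital discharge and is not a general licence.
- A stay that begins and ends before Visit 1 was due is uncounted in both arms anyway. Only stays that straddle the due date, or fall inside an extension already granted, matter.
- The Run-In tests require 3 weeks without exacerbation in both groups, which delays Control visits too, although tests from the 3 months before randomisation may be reused.
- Run-In length is tabulated by group (section 7.B.3.7), and serious adverse events are listed from Selection with their period, so an imbalance would be visible. That describes it but does not give a corrected endpoint.
- Starting the count after the training phase is a deliberate choice. A fixed start at day 35 largely keeps it.

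A reader might infer three stronger things that the protocol does not support:

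- **That Visit 1 is held open until the four sessions are done.** The COPD Education text caps them at 5 weeks, and section 3.D makes inability to follow them before Visit 1 a reason to discontinue the strategy.
- **That investigators are given the decision to extend.** The protocol does not say who decides. It is an inference from their scheduling Visit 1.
- **That the type I error is materially inflated.** Figures of that kind need extreme one-sided scenarios. Suppose 15% of patients have a stay near Visit 1, on top of 1.2 other admissions a year with a mean stay of 10 days, and 50% or 80% of these stays are moved out in the Intervention group and none in Control. Rejection is then about 8% or 14%. At that admission rate only 1.2 × 10 / 365 = 3.3% of patients are in hospital on a given day. If all of these were moved in one arm and none in the other, rejection is 5.4%. With 15% affected and 50% versus 25% moved, it is 6.1%.

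**Conclusion.** The design weakness is real and modest. The protocol ties the primary count to a visit date that can move after randomisation, for reasons that include events of the endpoint's own kind and a purpose present in one arm only. Unequal use would bias the comparison, and neither the scaling to 365 days nor the blinded review would correct it. Equal use would not bias it.

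Under the assumed rates with timing modelled, the bias is about 0 to 1 day per year against the planned 10, with little or no effect on the type I error. These sizes rest wholly on assumed admission rates, stays and extension frequencies. They are a sensitivity range and not a forecast.

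Separately, the extension granted for the sessions (section 4.B.3.1), the 5-week limit on those sessions (COPD Education) and the arm-neutral footnote (section 6.E) do not agree.

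**What to change.** 1. Pre-specify a count of unscheduled hospital days from the same fixed time after randomisation in both arms, whatever the date of Visit 1: for example from randomisation + 35 days, for a fixed length. It should be at least a sensitivity analysis of the primary criterion.
2. Tabulate by arm how often the Run-In was extended and why.
3. Reconcile the three passages on extension grounds and session timing. Which rule should apply is for the sponsor to settle.

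**Cost.** Wording in the protocol and analysis plan, and little new data. Admissions from Visit 0 are already reported as serious adverse events (sections 6.B and 8.B), and admission and discharge dates are recorded for exacerbations throughout the study (section 6.A.2.2). Run-In admissions would need the same details as later ones, namely type of facility and whether scheduled. In patients with an extended Run-In, some days before the programme is fully delivered would be counted.
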